The aim of this study is to generate evidence to support vaccination of COPD patients with PCV13 and/or against influenza in terms of clinical benefits and quality of life.

2.1 **STUDY DESIGN**

Prospective observational study, which will be carried out in 6 different geographical areas in Spain (Salamanca, Cantabria, Palma de Mallorca, Madrid, Barcelona and Seville), involving 1 hospital in each region.

Subjects identified with COPD will be invited to participate by investigators at the time of their routine follow-up visits. All therapies will be prescribed in line with routine clinical practice according to the updated National COPD Guidelines (GesEPOC),¹ indicating among other therapies active reduction of risk factors, and influenza and pneumococcal vaccination (with PCV13) in all patients with mild, moderate or severe COPD. All patients will be advised to quit smoking and recommended healthy lifestyle habits.

Study will include periodic visits for all patients, to complete a total follow up of 2 years.

2.2 **STUDY OBJECTIVES**

The study objectives are to:

- **Primary objectives**

1. Evaluate the impact of routine clinical practice vaccination with PCV13 on the reduction of the risk of moderate/severe COPD exacerbations, after 2 years of follow-up.
2. Determine which subgroup of patients (based on the severity of COPD) benefit most from vaccination with PCV13

COPD severity (GOLD)¹⁸

- GRADE 1: Mild/unknown [$FEV1 \geq 80\%$, $FEV1/FVC < 0.7$ or no spirometry record]
- GRADE 2: Moderate [$50\% \leq FEV1 < 80\%$, $FEV1/FVC < 0.7$]
- GRADE 3: Severe [$30\% \leq FEV1 < 50\%$, $FEV1/FVC < 0.7$]
- GRADE 4: Very severe [$FEV1 < 30\%$ or $FEV1 < 50\%$ plus respiratory failure, $FEV1/FVC < 0.7$])

- **Secondary objectives**

1. Evaluate the impact of influenza and PCV13 vaccination on the reduction of the risk of exacerbations
2. Evaluate the impact of vaccination with PCV13 on patients' quality of life
3. Evaluate the impact of vaccination with PCV13 on the decrease in FEV1
4. Estimate the potential savings for the healthcare system derived from vaccination of COPD patients with PCV13
5. Determine the prevalence of PCV13 vaccination in COPD patients.

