4 HYPOTHESIS AND ROLE OF DISCUSSION

The statistical significance value is set at $p < 0.05$. The SPSS statistical package version 19.0 or later will be used.

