- For comparison of independent samples, the Pearson's Chi-squared test or the Fisher's exact test for 2x2 tables or likelihood ratio for mXn tables will be used for qualitative variables. The Student's t-test, one-way ANOVA or its non-parametric equivalents, the Mann-Mann U test or Kruskal-Wallis H test, will be used for quantitative variables.
- For comparison of paired samples, the McNemar's test will be used for qualitative variables and the Student's t-test or Wilcoxon's test for quantitative variables.
- The study will seek to identify factors associated with the occurrence of exacerbations throughout the follow-up period; to that end, a multivariate logistic regression analysis will be performed, where the dependent variable will be the occurrence of exacerbations (Yes/No) during the study. Vaccination with PCV13 and significant variables in the univariate model will be used as possible risk factors: demographic characteristics, influenza vaccination, smoking habit, etc. In addition, potential confounding variables will be considered: exacerbator phenotype, comorbidities, COPD severity, FEV1 (no control possible based on the study design).
- Appropriate tests will be performed accordingly to determine if the necessary requirements are fulfilled for the use of parametric tests.
- Estimates will be performed with a 95% confidence interval. The SPSS statistical package, version 19.0 or later, will be used.

8.2 **STATISTICAL ANALYSIS**

8.2.1 **Patient disposition**

The absolute and relative frequency of evaluable patients will be determined. In the subpopulation of non-evaluable patients, the frequency distribution will be presented based on the reasons for non-evaluation:

- Patient under 18 years of age at the time of obtaining informed consent
- Not diagnosed with COPD of any grade (patients diagnosed with COPD less than 2 years after inclusion in the study should not be included)
- At least two years of prior medical records are not available relating to (if applicable):
 - History of moderate/severe exacerbations
 - History of influenza vaccination (date)
 - History of pneumococcal vaccination (date)
 - Comorbidities
 - Previous treatments
- No spirometry data available
- Inability to understand and complete the required quality of life questionnaires
- No evidence of a personally signed and dated informed consent document indicating that the subject has been informed of all pertinent aspects of the study

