The Student's t test, one-way ANOVA or its non-parametric equivalents, the Mann-Mann U test or Kruskal-Wallis H test will be used to determine if statistically significant differences are observed in NEPA, NEPA Mild, NEPA Moderate, NEPA Severe and NEPA Moderate/Severe according to the severity of COPD and type of patient (exposed/unexposed). In order to determine the impact of PCV13 vaccination on exacerbations, paired data comparisons will be made between (NEPA_pre_PCV13 vs. NEPA_post_PCV13) and (NEPA_pre_PCV13 (moderate/severe) vs. NEPA_post_PCV13 (moderate/severe)), using the Student's t-test for paired data or its non-parametric equivalent, the Wilcoxon test.

In order to study which subgroups of patients obtain a greater benefit from vaccination

with PCV13 according to COPD severity, paired data comparisons will be made between (NEPA_pre_PCV13 vs. NEPA_post_PCV13) and (NEPA_pre_PCV13 (moderate/severe) vs. NEPA_post_PCV13 (moderate/severe)), in each of the four patient subpopulations established based on disease severity.

In order to determine the factors associated with the presence of an exacerbator patient, a logistic regression model will be constructed, whose dependent variable is (exacerbator/non-exacerbator patient) and, as independent variables, all those possible factors that have been significant in the univariate models ($p_{value} < 0.25$), following the methodology of Hosmer-Lemeshow.

- ❖ Vaccine exposure (PCV13 yes/no)
- ❖ COPD severity (Grade I, Grade II, Grade III, Grade IV)
- ❖ Age
- ❖ Sex
- ❖ Time since diagnosis of the disease
- ❖ Patient with stable treatment for at least three months
- ❖

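### Primary objective 2 rests on eight unadjusted per-grade tests: if no grade has any true before/after change, the chance of at least one significant result is 18.5% to 33.7%

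*SAP*

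**What the plan says.** SAP 2.2 lists as its second primary objective: "Determine which subgroup of patients (based on the severity of COPD) benefit most from vaccination with PCV13". Protocol 7 lists the same objective as primary, and neither document calls it exploratory.

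SAP 8.2.3.1 gives the analysis. It opens with the purpose, "In order to study which subgroups of patients obtain a greater benefit from vaccination", and then specifies paired comparisons of the pre- and post-PCV13 rates (the NEPA indices) "in each of the four patient subpopulations established based on disease severity". Two indices are compared in each grade: all exacerbations, and moderate/severe exacerbations. The test is named just before this, for the overall comparison: "using the Student's t-test for paired data or its non-parametric equivalent, the Wilcoxon test". I take it to apply within grades too. Protocol 8.7 describes no per-grade test, so the SAP text is the only rule.

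On error control, SAP 4 is brief: "The statistical significance value is set at" p < 0.05. SAP 8.1 adds: "Estimates will be performed with a 95% confidence interval". Neither document mentions an adjustment, a hierarchy, a gate on the overall result, or which of the two indices decides objective 2.

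**The concern.** Eight tests at 0.05 serve one primary objective, and nothing limits the chance that at least one of them is significant by luck. The four grades and two indices give a reader eight opportunities to find a grade that appears to benefit. The SAP does not say in advance which would count.

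The all-severity index adds to this. Objective 1 concerns moderate/severe exacerbations, and SAP 6 states the two objectives together in those terms. Testing all exacerbations by grade as well enlarges the family without being needed for the stated question.

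What is at stake is how a single per-grade p < 0.05 can be read. SAP 2 says larger studies are needed to assess which subgroups might benefit most, so such a result is likely to be taken as evidence about that grade. Under the present plan it would carry much less weight than a 5% test suggests.

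**Working it through.** Neither document states a familywise error rate, so there is no planned figure to reproduce.

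**Inputs**
- Level per test: 0.05 (SAP 4). Sidedness is not stated. Two-sided is assumed, which fits the 95% intervals in SAP 8.1.
- Grades: 4. Indices per grade: 2. Tests: 4 × 2 = 8 (SAP 8.2.3.1).
- Independence across grades holds if each patient is in one grade only. As worded in SAP 5.4, a patient with FEV1 from 30% to below 50% plus respiratory failure fits both grade 3 and grade 4, so this needs a rule.
- Correlation between the two test statistics within a grade: not given. The range 0 to 1 is shown. All exacerbations include the moderate/severe ones, so the correlation should be clearly positive.
- Null: no true before/after change in any grade, from any cause, with each test holding 5%.

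**Limits of the range, either direction**
- Fully correlated indices, four tests in effect: 1 − 0.95^4 = 18.5%
- Independent indices, eight tests: 1 − 0.95^8 = 33.7%

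**Limits of the range, benefit direction only (0.025 per test)**
- Four tests in effect: 1 − 0.975^4 = 9.6%
- Eight tests: 1 − 0.975^8 = 18.3%
- A single test, for comparison: 2.5%

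**Between the limits**

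The two statistics in a grade are taken as bivariate normal with correlation r. The familywise rate is 1 − q^4, where q is the probability that neither test in a grade is significant. For the benefit column, q is the probability that neither exceeds 1.96 in that direction.

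| r | At least one in a grade (1 − q) | Any of four grades, either direction | Any of four grades, benefit direction |
|---|---|---|---|
| 0 | 9.75% | 33.7% | 18.3% |
| 0.5 | 9.07% | 31.7% | 17.0% |
| 0.7 | 8.35% | 29.4% | 15.7% |
| 0.9 | 7.04% | 25.3% | 13.4% |
| 0.95 | 6.46% | 23.4% | 12.3% |
| 1 | 5.00% | 18.5% | 9.6% |

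**Sensitivity to the null**

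The tests use vaccinated patients only, so a drift unrelated to the vaccine shifts them. As an illustration, assume a drift of one standard error in every grade.
- Either direction: each test is significant with probability 0.170, so four tests give 1 − (1 − 0.170)^4, about 53%.
- If the drift is towards harm, a false benefit has probability about 0.0015 per test, so four tests give 1 − (1 − 0.0015)^4, about 0.6%.

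**Definition check**

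SAP 8.2.3.1 writes the numerator of the post-vaccination moderate/severe index as events before PCV13. Taken literally, four of the eight tests compare the same events over two different time spans and cannot be assumed to hold 5%. The figures above apply only once that definition is reconciled.

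**After the fix**

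The smallest of four p-values is set against 0.05/4 = 0.0125. The chance of any false result is 1 − (1 − 0.0125)^4 = 4.9%.

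**The case against.** The strongest objection is that the size is easily overstated. Three parts of it stand.

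- A reader might infer that these rates apply whenever the vaccine has no effect. They do not. The tests compare before with after, so progression, regression to the mean or uneven ascertainment can produce a change without any vaccine effect. The rates hold only if nothing changes for any reason.
- A reader might also infer that such bias can only add to the rates. For a false finding of benefit that is unsupported. The pre-vaccination period runs from COPD diagnosis (SAP 8.2.3.1 footnote), while Protocol 8.2.1 requires only two years of records. If earlier events are missed, the pre-vaccination rate is diluted and the vaccine looks worse. Other biases could act the other way.
- The upper end of the range needs independent indices, which is implausible when one contains the other. A range that stops at a correlation of 0.9 would leave out the lower values, down to 18.5%.

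A further tempting reading is that a significant grade would be used to direct vaccination to that subgroup. The documents do not say so. The stated aim is evidence to support vaccinating COPD patients, and vaccination follows a guideline covering mild, moderate and severe disease. Nor does the SAP state a rule that p < 0.05 in a grade amounts to a claim.

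It can also be said that this is an observational study with confidence intervals already planned, and that labelling the per-grade p-values exploratory would suffice. That would be coherent, but the SAP does not do it, and it lists the objective as primary. Finally, per-grade tests do not compare grades, however they are adjusted. That is correct, but it is a separate point: these eight p-values would still be reported at 0.05.

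**Conclusion.** The concern holds. The SAP addresses a primary objective with eight paired tests at 0.05, with no multiplicity control and no designated index. The chance of at least one significant grade result is 18.5% to 33.7%. In the benefit direction it is 9.6% to 18.3%, so even the lower limit is nearly four times the 2.5% of a single test.

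This rests on four assumptions: no true before/after change in any grade for any reason, each test holding its 5%, two-sided testing, and patients assigned to one grade only. The correlation between the indices is unknown, and the top of each range is unlikely. Before/after bias could move the rates up or down. The figures are therefore not the false-positive rate under an ineffective vaccine.

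**What to change.** 1. First reconcile the SAP 8.2.3.1 definition of the post-vaccination moderate/severe index, whose numerator is written as events before PCV13. The remaining steps depend on this.
2. In SAP 8.2.3.1, name the moderate/severe index as the only one used for per-grade claims under objective 2.
3. State a rule that puts each patient in exactly one GOLD grade.
4. Apply Holm's procedure to the four per-grade tests, with the smallest p-value set against 0.0125.
5. Report the all-severity index by grade as estimates with 95% confidence intervals, without a claim.

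This needs SAP wording only, with no new data or patients. The price is power for a claim in a single grade. A test with 80% power at 0.05 has about 62% at 0.0125: 1.960 + 0.842 − 2.498 = 0.304, and the normal probability below 0.304 is 0.62.

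The change controls chance error across grades. It does not remove before/after bias, and it does not show that one grade benefits more than another, which needs a direct comparison between grades.

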#### **8.5. Study size**

With 35% patients vaccinated with PCV13, enrolling 1540 eligible COPD patients will provide approximate 540 patients in PCV13 cohort and 1000 patients in the control cohort.

Assuming 37% of the control patients experiencing moderate/severe exacerbation per year with 70% of the patients remaining in the study at year 1, this sample size will provide 91% power to detect a statistical significant reduction of 10% on COPD moderate/severe exacerbations from PCV13 after 1-year. Assuming additional 30% dropout from year 2, the study sample size will provide 91% power to detect a statistical significant reduction of 14% on COPD moderate/severe exacerbations from PCV13 after 2-year.

Time	PCV13		Control		Power	Retention Rate
	Sample Size	% exacerbation	Sample Size	% exacerbation		
Enrollment	540		1000			
1-year	378	27%	700	37%	91.43%	70% from Enrollment
2-Year	264	60%	490	74%	91%	70% from Year 1

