## **8.7. Data analysis**

Depending on recruitment and data availability an interim analysis may be performed after the first year, if at least 75% of subjects included have completed one year of follow up.

- To determine the impact of PCV13 vaccination, the incidence of exacerbations will be determined 2 years after the inclusion in the study and will be compared with the incidence 2 years before the study (2 years of clinical history required including records of previous moderate/severe exacerbations, influenza and pneumococcal vaccination history comorbidities and previous treatments)
- A descriptive analysis of all variables will be performed. Qualitative variables will be analyzed by absolute and relative frequencies. Quantitative variables will be studied by the usual centralization and dispersion measures (mean, median, standard deviation, confidence intervals, minimum, maximum and interquartile range).
- For comparison of independent samples, the Pearson chi-squared test or the exact Fisher test for 2x2 tables or likelihood ratio for mXn tables, for qualitative variables, will be used. The Student's t test, one-way ANOVA or its non-parametric equivalent U-Mann-Mann, H-Kruskal-Wallis for quantitative variables will be used.
- For comparison of paired samples, the McNemar's test will be used for qualitative variables and Student's t test or Wilcoxon's test for quantitative variables.
- A multivariate logistic regression analysis will be performed, in order to identify risk factors associated with exacerbations. Exacerbations existence (yes/no) will be used as dependent variable. Vaccination with PCV13 and statistically significant variables in the univariate model, will be used as possible risk factors: demographic characteristics, influenza vaccination, smoking habit, etc. In addition, potential confounding variables will be considered: phenotype, comorbidities, COPD severity, FEV1 (no control possible based on the study design)
- Appropriate tests will be performed accordingly to determine if the necessary requirements are fulfilled for the use of parametric contrasts.
- Estimates will be performed with a 95% confidence interval. The SPSS statistical package version 19.0 or later will be used.

Redacted

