8.2.3 Effectiveness analysis

8.2.3.1 Study of exacerbations

A detailed analysis of the total number of exacerbations reported by the study patients will initially be performed. The absolute and relative frequency of patients who have reported at least two moderate exacerbations or one severe exacerbation per year (exacerbator patient) will be given.

The following indices will be calculated:

- NEPA (number of exacerbations patient/year) = Total no. of exacerbations reported by patients/ Patient follow-up time^{*)}
- NEPA Mild = Total no. of mild exacerbations/Patient follow-up time
- NEPA Moderate = Total no. of moderate exacerbations/Patient follow-up time
- NEPA Severe = Total no. of severe exacerbations/Patient follow-up time
- NEPA Moderate/severe = Total no. of moderate_severe exacerbations/Patient follow-up time

The following will also be calculated in the subpopulation of exposed patients:

- NEPA_pre_PCV13 = Total no. of exacerbations reported by the patient prior to receiving the PCV13 / Time to vaccination with PCV13^{**)}
- NEPA_pre_PCV13 (moderate/severe) = Total no. of moderate/severe exacerbations reported by the patient prior to receiving the PCV13 / Time to vaccination with PCV13^{**)*)}
- NEPA_post_PCV13 = Total no. of exacerbations reported by the patient after receiving the PCV13 / Time since vaccination with PCV13^{***)}
- NEPA_post_PCV13 (moderate/severe) = Total no. of moderate/severe exacerbations reported by the patient prior to receiving the PCV13 / Time since vaccination with PCV13^{***)}

*) Time from the date of COPD diagnosis to the date of the last follow-up visit. If the date of diagnosis of the disease is unknown, it will be computed as two years before the date of inclusion of the patient in the study

**) Time from date of COPD diagnosis to date of PCV13 vaccination

***) Time from vaccination with PCV13 to date of the last follow-up

Each of the indices calculated above will be described using the main measures of central tendency and dispersion (mean, median, standard deviation, confidence intervals, minimum, maximum and interquartile range).

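### Neither covariate-adjusted PCV13 model uses the exacerbation count or follow-up time; the power lost runs from negligible to substantial, depending on inputs the plan does not give

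*SAP*

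**What the plan says.** **What is recorded.** Protocol 8.3 collects the number and severity of exacerbations, Protocol Table 1 asks for them at every contact, and SAP 6 lists them under the primary endpoint.

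**Adjusted model A.** SAP 8.1 plans a multivariable logistic regression in which "the dependent variable will be the occurrence of exacerbations (Yes/No) during the study". Protocol 8.7 plans the same: "Exacerbations existence (yes/no) will be used as dependent variable".

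**Adjusted model B.** In SAP 8.2.3.1 "a logistic regression model will be constructed, whose dependent variable is (exacerbator/non-exacerbator patient". An exacerbator is a patient with "at least two moderate exacerbations or one severe exacerbation per year (exacerbator patient". The SAP gives no source or reason for this threshold and does not say how the annual criterion applies over two years. PCV13 is one of the candidate factors, which enter on a univariate p below 0.25.

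**Where the count is used.** SAP 8.2.3.1 defines NEPA as exacerbations divided by follow-up time. It compares NEPA between exposed and unexposed patients and across severity grades by t-test, ANOVA or rank tests, and before versus after PCV13 by paired tests. None of these has covariates. No Poisson, negative binomial or other rate regression appears in either document.

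**Sizing.** Protocol 8.5 and SAP 5 size the study on the percentage of patients with a moderate/severe exacerbation, starting from "approximate 540 patients in PCV13 cohort and 1000 patients in the control cohort".

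**The concern.** Vaccination here follows routine practice, and Protocol 8.1 draws the controls from patients who were not recommended PCV13, did not take it up or had a contraindication. An unadjusted comparison cannot separate the vaccine from those reasons, so adjustment matters. Yet the plan offers the count without adjustment, or adjustment without the count, and never both.

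The yes/no outcomes discard information. Under the exacerbator rule, a patient with one moderate event in the year scores the same as a patient with none, and two moderate events score the same as six. Under the any-event rule, one event scores the same as ten. Neither logistic model accounts for time observed, although the plan expects only 0.70 × 0.70 = 49% of patients to remain at two years. At stake are the power and precision of the adjusted PCV13 estimate.

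**Working it through.** **Inputs from the documents.** "The statistical significance value is set at" p < 0.05 (SAP 4). Sidedness is not stated; two-sided is assumed because "Estimates will be performed with a 95% confidence interval" (SAP 8.1). With "70% of the patients remaining in the study at year 1" (Protocol 8.5), the 1-year row is 378 PCV13 v 700 control, 27% v 37%. The 2-year row is 264 v 490, 60% v 74%.

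**Inputs assumed, because the documents give none.** Dispersion k = 0 (Poisson) to 2; severe share s of moderate/severe events = 10 to 50%. Follow-up is taken as equal, with no covariates.

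**Step 1: the plan's own figure.** Two-proportion normal test, pooled variance under the null:
- pooled proportion = (378×0.27 + 700×0.37)/1078 = 0.335
- null SE = √(0.335×0.665×(1/378 + 1/700)) = 0.0301
- alternative SE = √(0.27×0.73/378 + 0.37×0.63/700) = 0.0292
- power = Φ((0.10 − 1.96×0.0301)/0.0292) = Φ(1.40) = 91.9%

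The plan states 91.43%, so the 1-year row reproduces.

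**Step 2: formulas.** The mean m per patient is set so that P(at least one event) equals the plan's percentage: m = −ln(1−p) for k = 0, otherwise m = ((1−p)^(−k) − 1)/k.
- Count model: Wald test of ln(m1/m0), variance (1/m1 + k)/n1 + (1/m0 + k)/n0.
- Exacerbator in one year: P = 1 − E[exp(−mg)(1 + (1−s)mg)], with g a gamma variable of mean 1 and variance k; then the test in Step 1.
- Exacerbator in any one of two years, m being the annual mean: P = 1 − E[exp(−2mg)(1 + (1−s)mg)²].

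**Step 3: one cell in full (1 year, k = 1, s = 20%).** m = 0.370 v 0.587, rate ratio 0.63.
- Count: SE = √((1/0.370 + 1)/378 + (1/0.587 + 1)/700) = 0.117; |ln 0.63| = 0.462; power = Φ(0.462/0.117 − 1.96) = 97.7%.
- Exacerbator: 11.2% v 18.4%, power 87.8%. Loss about 10 points.

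**Step 4: 1-year row.**

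| k | Rate ratio | Count | Any event (loss) | Exacerbator, s = 10–50% (loss) |
|---|---|---|---|---|
| 0 | 0.68 | 94.7% | 91.9% (2.8) | 69–79% (16–26) |
| 0.5 | 0.66 | 96.5% | 91.9% (4.5) | 82–84% (12–15) |
| 1 | 0.63 | 97.7% | 91.9% (5.8) | 88–89% (9–10) |
| 2 | 0.58 | 99.1% | 91.9% (7.2) | 92–94% (5–7) |

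A 4,000-replicate simulation (s = 10% and 30%) agreed: count 96–99.5%, exacerbator 70–94%.

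**Step 5: 2-year row as stated.** The any-event outcome has 97.5% power. The plan states 91%, which this row does not reproduce. The count model has 99.9–100%, so any event loses about 2–3 points. Exacerbator in any one year has about 96–99.9% and loses about 0–4 points. If the criterion is instead read as a mean annual rate over two years, simulation gave a loss of 0 to 48 points.

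**Step 6: 1-year rates carried forward, 264 v 490.** The stated 74% is 2 × 37%; two independent years at 37% would give 1 − 0.63² = 60.3%. The stated row implies a control mean over two years of 1.35 events at k = 0 (2.85 at k = 1), against 0.92 (1.17) from doubling the 1-year mean. The two rows therefore do not share one constant rate. With the 1-year rates carried forward:

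| k | Any event, PCV13 v control | Power | Count | Loss |
|---|---|---|---|---|
| 0 | 46.7% v 60.3% | 94.8% | 98.9% | 4 |
| 0.5 | 44.4% v 56.7% | 90.0% | 98.5% | 8–9 |
| 1 | 42.5% v 54.0% | 85.5% | 98.4% | 13 |
| 2 | 39.7% v 50.2% | 79.1% | 98.7% | 20 |

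Exacerbator in any one year has 82–89%, a loss of about 10–17 points.

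**The case against.** Primary objective 1 is set at two years, and on the plan's own 2-year row every option except the mean-rate reading of exacerbator has high power. That stands: at that stated effect the yes/no outcomes cost little. The reassurance is weakened because that row does not follow from the 1-year rate (Step 6).

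The high end of the range needs k = 0, meaning no variation between patients, together with a 10% severe share; at k = 1 to 2 the 1-year exacerbator loss is 5–10 points. That stands too. Holding P(at least one event) fixed also makes the assumed rate ratio fall from 0.68 to 0.58 as k rises. With the ratio held at 0.68, the 1-year exacerbator loss is 14–26 points. All figures are unadjusted, although the point concerns adjusted models.

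Four stronger readings are tempting, and the documents do not support them.
- A reader might apply 5–26 points to both models. It belongs to the exacerbator model at one year; any event loses about 3–7 there.
- A reader might call exacerbator the worse outcome throughout. At k = 2 it has 92–94% power at one year against 91.9% for any event, and at two years it can lose less.
- A reader might infer that the GOLD subgroups are hit harder. SAP 8.2.3.1 answers the subgroup question with paired NEPA rates within each grade; in model B, grade is a listed covariate.
- A reader might say that the adjusted model carries the conclusion on PCV13. SAP 8.2.3.1 assigns the impact of vaccination to paired NEPA comparisons, and both logistic models are described as a search for associated factors. Adjustment is needed because vaccination is not randomised, but the plan does not give these models that role.

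**Conclusion.** The structural point holds without assumptions: neither adjusted model that considers PCV13 uses the recorded count or the follow-up time, and the rates that do use them are compared without covariates.

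The size of the loss is an assumption-based range (k = 0–2, severe share 10–50%, two-sided 0.05, equal follow-up):

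| Inputs | Any event | Exacerbator |
|---|---|---|
| 1-year row | about 3–7 points | about 5–26 points |
| 2-year row as stated | about 2–3 | about 0–4 (in any one year) |
| 1-year rates carried to 2 years | about 4–20 | about 10–17 (in any one year) |

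The documents do not show that an effect of the planned 2-year size would be missed. They do leave the adjusted analysis exposed to a material loss under plausible inputs that they do not settle. A model that avoids it uses data already collected, so the change should be made.

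**What to change.** In SAP 8.2.3.1 and 8.1, and in Protocol 8.7, add an adjusted negative binomial regression, or a Poisson regression with robust standard errors, specified as follows.
- Outcome: number of moderate/severe exacerbations.
- Offset: log observed person-time, counted from study inclusion to last follow-up (not from COPD diagnosis, as NEPA does).
- Exposure: PCV13 forced in, not subject to the p < 0.25 screen. Time up to 15 days after PCV13 counts as unvaccinated, in line with the definition under Protocol Table 1. A patient vaccinated during follow-up then contributes both kinds of time, so standard errors should be clustered by patient.
- Covariates: the same as in the logistic models.
- Report: adjusted rate ratio with 95% CI.

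Keep both logistic models as supportive, and state how the annual exacerbator criterion applies over two years.

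**Cost.** SAP wording and a matching change to Protocol 8.7; under the last paragraph of that section, an amendment is needed if this counts as a major change to the primary analysis. No new data, visits or patients: exacerbation onset is already defined, and NEPA before and after PCV13 already needs the vaccination date. SPSS fits these models. The downsides are small: the model needs a dispersion assumption, which robust standard errors relax, and very frequent exacerbators carry more weight, which the retained logistic models would reveal.
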